13.5. Planned Listing Descriptions

The following are planned data and subject data listings for protocol number PH94B-CL032.

In general, 1 listing will be produced per eCRF domain. All listings will be sorted by treatment, site, and subject number. All calculated variables will be included in the listings.

In all listings a blank line will be placed between each subject. Within a data listing, if an item appears line after line (e.g., repetition of subject number), then only the first occurrence will be displayed. Screen failures will only be presented in Listings 16.2.1.1, 16.2.2.1, and 16.2.2.3; otherwise, only enrolled subjects will be listed.

In data listings, the information for 1 subject will be kept on 1 page, if at all possible, rather than splitting a subject's information across pages.

Table 7: Planned Listings

Listing Number	Population	Listing Title / Summary
16.2 Subject Data Lis	tings	
16.2.1 Subject Discon	tinuations/Completions	
Listing 16.2.1.1	All Subjects	Subject Disposition
16.2.2 Protocol Devia	tions	
Listing 16.2.2.1	All Subjects	Inclusion and Exclusion Criteria
Listing 16.2.2.2	All Enrolled Subjects	Protocol Deviations
Listing 16.2.2.3	Screen Failures	Reasons for Screen Failures
16.2.3 Patients/Subject	cts Excluded from the Effic	cacy Analyses
Table 16.2.3.1	All Subjects	Analysis Populations
16.2.4 Demographic I	Data and Other Baseline Cl	haracteristics
Listing 16.2.4.1	All Subjects	Subject Consent and Demographics
Listing 16.2.4.2	All Subjects	Medical and Psychiatric History
Listing 16.2.4.3	All Subjects	Mini-International Neuropsychiatric Interview (MINI)
Listing 16.2.4.4	All Subjects	

Listing Number	Population	Listing Title / Summary
16.2 Subject Data Lis	tings	
16.2.5 Compliance an	d/or Drug Concentration	Data
Listing 16.2.5.1	All Subjects	Study Drug Dispensation
Listing 16.2.5.2	All Subjects	Study Drug Administration
16.2.6 Individual Effi	cacy Response Data	•
Listing 16.2.6.1	All Subjects	Subjective Units of Distress Scale (SUDS)
Listing 16.2.6.2	All Subjects	Clinical Global Impression – Improvement scale (CGI-I)
Listing 16.2.6.3	All Subjects	Patient Global Impression of Change (PGI-C)
Listing 16.2.6.4	All Subjects	Liebowitz Social Anxiety Scale (LSAS)
Listing 16.2.6.5	All Subjects	
16.2.7 Adverse Event	Listings (by Subject)	
Listing 16.2.7.1	All Subjects	Adverse Events
16.2.8 Laboratory Va	lues (by Subject)	
Listing 16.2.8.1	All Subjects	Hematology Laboratory Evaluations
Listing 16.2.8.2	All Subjects	Clinical Chemistry and Thyroid Laboratory Evaluations
Listing 16.2.8.3	All Subjects	Urinalysis Laboratory Evaluations
Listing 16.2.8.4	All Enrolled Female Subjects	Pregnancy Test Results
Listing 16.2.8.5	All Subjects	Laboratory Results for Drug Screening
16.2.9 Other Clinical	Observations and Measur	ements (by Subject)
Listing 16.2.9.1	All Subjects	Vital Signs
Listing 16.2.9.2	All Subjects	12-Lead Electrocardiogram Measurements
Listing 16.2.9.3	All Subjects	Physical Examination Measurements
Listing 16.2.9.4	All Subjects	Quick Olfactory Test (QOT)
Listing 16.2.9.5	All Subjects	Prior and Concomitant Medications
Listing 16.2.9.6	All Subjects	Columbia Suicide Severity Rating Scale (C-SSRS) Screening
Listing 16.2.9.7	All Subjects	Hamilton Depression Rating Scale (HAM-D)
Listing 16.2.9.8	All Subjects	
16.2.10 Other Study	Measurements or Assessm	ents (by Subject)
Listing 16.2.10.1	All Subjects	COVID-19 Impact Assessment

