2.2. Schedule of Events

Table 2-1: **Schedule of Events**

Assessment	Screening Day -35 to -3 Visit 1	Baseline Day 0 Visit 2	Treatment Day 7 (± 2 days) Visit 3	Follow-up Day 14 (± 2 days) Visit 4
Written Informed Consent	X			
Subject Demographics	X			
Urine Drug Screen (Instant Exam, on site)	X	X	X	X
Urine Pregnancy Test	X	X	X	X
MINI	X			
Medical and Psychiatric History	X			
Prior and Concomitant Medication Recording	X	X	X	X
LSAS	X			X
Hamilton Depression Scale	X			X
C-SSRS	X	X (end of visit)c	X (end of visit)c	X
Physical Examination and Examination of Nasal Passages	X	30 To	V	X
Vital Signs	X	X	X	X
Electrocardiogram	X			X
Blood Tests and Urinalysis	X			X
Inclusion/Exclusion Review	X	X		
Investigational Product Administration Training	X			
Investigational Product Administration		X	X	
Public Speaking Challenge ^b		X	X	
Randomization			X	
PGI-C Scale			X	
CGI-I Scale			X	
Adverse Events Recording		X	X	X

Abbreviations: C-SSRS = Columbia Suicide Severity Rating Scale; CGI-I = Clinical Global Impression of Improvement; LSAS = Liebowitz Social Anxiety Scale;

PGI-C= Patient Global Impression of Change;

Amendment 3, Version 4.0 12-Aug-2022 Page 10 of 101

3.	TAE	BLE OF CONTENTS	
1.	APP	ROVAL SIGNATURES	2
2.	PRO	TOCOL SUMMARY	4
	2.1.	Synopsis	4
	2.2.	Schedule of Events	10
3.	TAB	BLE OF CONTENTS	12
	3.1.	List of In-Text Tables	16
	3.2.	List of In-Text Figures	16
RE	ASON	NS FOR AMENDMENT	17
SU	MMA	RY OF AMENDED SECTIONS	18
AN	1END	ED PROTOCOL	20
4.	LIST	Γ OF ABBREVIATIONS AND DEFINITION OF TERMS	21
5.	INT	RODUCTION	22
	5.1.	Background and Rationale	22
		5.1.1 Social Anxiety Disorder	22
		5.1.2 Nasal Chemosensory Systems	22

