9.7.2 Prohibited Therapies

With the exception of concomitant medications for the treatment of insomnia described in Section 9.7.1, no other psychotropic medication besides IP is permitted to be used by any subject between Screening (Visit 1) and Follow-up (Visit 4). At Visit 1, the investigator should consider checking the local Prescription Drug Monitoring Database to verify the lack of use of scheduled central nervous system active drugs, such as benzodiazepines.

Prior use of PH94B is not permitted.

Where washout of prohibited medications is required before Baseline (Visit 2), tapering rates are at the discretion of the Investigator and are to be determined on an individual basis, with consideration to subject state, dose, and known pharmacokinetics of the medication being discontinued. The subject must be consented before any tapering is started.

AD-MW-07.08 18-Jun-2019 Page 38 of 101

12-Aug-2022

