11.2. Event Assessment and Follow-up of Adverse Events

The occurrence of an AE or SAE may come to the attention of study personnel during study visits and interviews of a study subject presenting for medical care, or upon review by a study monitor.

All AEs including local and systemic reactions not meeting the criteria for SAEs will be captured on the appropriate eCRF. Information to be collected includes event description, time of onset, clinician's assessment of severity, relationship to study product (assessed only by those with the training and authority to make a diagnosis), and time of resolution/stabilization of the event. All

Page 54 of 101

Amendment 3, Version 4.0

12-Aug-2022

AEs occurring while on study must be documented appropriately regardless of relationship. All AEs will be followed to adequate resolution.

Any medical condition that is present at the time that the subject is screened will be considered as baseline and not reported as an AE. However, if the study subject's condition deteriorates at any time during the study, it will be recorded as an AE.

Changes in the severity of an AE will be documented to allow an assessment of the duration of the event at each level of severity to be performed. AEs characterized as intermittent require documentation of onset and duration of each episode.

The Investigator will record all reportable events with start dates occurring any time after informed consent is obtained until 7 days after the last day of study participation. At each study visit, the investigator will inquire about the occurrence of AE/SAEs since the last visit. Events will be followed for outcome information until resolution or stabilization.

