14.3. Screen Failures

Subjects who fail inclusion and/or exclusion criteria may be rescreened for the study. Subjects may only be rescreened once 30 days or more after the original Screening Visit. If a subject is eligible to enter the study after having previously failed screening, the subject will be assigned a new subject identification number.

Screen failures are defined as subjects who consent to participate in the clinical trial but are not subsequently entered in the study. A minimal set of screen failure information is required to ensure transparent reporting of screen failure subjects to meet the Consolidated Standards of Reporting Trials (CONSORT) publishing requirements and to respond to queries from regulatory authorities. Minimal information includes demography, screen failure details, eligibility criteria, and any SAE.

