2.2.2. Safety Endpoints

The safety endpoints are mapped to the safety objective as follows:

Safety Objective

The safety objective of the study is to determine safety and tolerability of PH94B compared to placebo in adult subjects with SAD from reported AEs and changes in vital signs, 12-lead ECGs, laboratory parameters, suicidality, level of depression, and physical examinations.

Safety Endpoints

Incidence and severity of AEs

Changes in vital signs results

Changes in clinical laboratory evaluation (hematology, chemistry, and urinalysis) results

Changes in 12-lead ECG results

Changes in physical examination findings

[figure not shown]
Mean HAM-D scores

[figure not shown]
Incidence of treatment-emergent suicidal ideation and behavior

3. Overall Study Design and Plan

3.1. **Overall Design**

The study is a Phase 3, multicenter, randomized, double-blind, placebo-controlled, parallel design, single-dose, clinical trial of the efficacy, safety, and tolerability of the acute administration of PH94B to relieve symptoms of acute anxiety in adult subjects with SAD.

Efficacy assessments for the primary endpoint will be completed at Visit 2 (Baseline) and Visit 3 (Treatment). Efficacy assessments for the secondary endpoint will be completed at Visit 3 (Treatment). Safety assessments are completed at Visit 1 (Screening) and Visit 4 (Follow-Up), with the exception of vital signs assessments, pregnancy tests, and Columbia-Suicide Severity Rating Scale (C-SSRS), which are completed at all visits, and AE recordings, which are completed starting at Visit 2 (Baseline). Refer to the Schedule of Events (Table 1) for more detail.

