13.3. Safety Data

Table 5: Safety Data

Table Number	Population	Table Title / Summary	
14.3.1 Displays of	Adverse Events		
Table 14.3.1.1	Safety	Overall Summary of Treatment Emergent Adverse Events	
Table 14.3.1.2.1	Safety	Treatment Emergent Adverse Events by System Organ Class and Preferred Term	
Table 14.3.1.2.2	Safety	Treatment Emergent Adverse Events by Preferred Term	
Table 14.3.1.3	Safety	Treatment Emergent Adverse Events by System Organ Class, Preferred Term, and Maximum Severity	

Fable Number Population		Table Title / Summary	
Table 14.3.1.4	Safety	Treatment Emergent Adverse Events by System Organ Class, Preferred Term, and Maximum Relationship to Investigational Product	
14.3.2 Summary	of Deaths, Other Se	erious and Significant Adverse Events	
Table 14.3.2.1	Safety	Treatment Emergent Adverse Events Leading to Study Discontinuation by System Organ Class and Preferred Term	
Table 14.3.2.2	Safety	Serious Treatment Emergent Adverse Events by System Organ Class and Preferred Term	
Table 14.3.2.3	Safety	Serious Treatment Emergent Adverse Events Related to Investigational Product by System Organ Class and Preferred Term	
14.3.3 Narratives	of Deaths, Other S	Serious and Certain Other Significant Adverse Events	
Table 14.3.3.1	Safety	Subject Listing of Serious Adverse Events	
Table 14.3.3.2	Safety	Subject Listing of Adverse Events Leading to Discontinuation of Investigational Product	
Table 14.3.3.3	Safety	Subject Listing of Adverse Events Leading to Death	
14.3.4 Abnormal	Laboratory Values	S :	
Table 14.3.4.1	Safety	Subject Listing of Abnormal Laboratory Values: Clinical Chemistry and Thyroid	
Table 14.3.4.2	Safety	Subject Listing of Abnormal Laboratory Values: Hematology	
Table 14.3.4.3	Safety	Subject Listing of Abnormal Laboratory Values: Urinalysis	
14.3.5 Laborator	y Data Summary T	ables	
Table 14.3.5.1.1	Safety	Clinical Chemistry and Thyroid: Observed Results and Change and Percent Change from Baseline by Study Visit	
Table 14.3.5.1.2	Safety	Clinical Chemistry and Thyroid: Shifts from Baseline Relative to the Normal Range	
Table 14.3.5.2.1	Safety	Hematology: Observed Results and Change and Percent Change from Baseline by Study Visit	
Table 14.3.5.2.2	Safety	Hematology: Shifts from Baseline Relative to the Normal Range by Study Visit	
Table 14.3.5.3.1	Safety	Quantitative Urinalysis: Observed Results and Change and Percent Change from Baseline by Study Visit	
Table 14.3.5.3.2	Safety	Qualitative Urinalysis: Summary of Results by Study Visit	

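### The start of AE recording is contradictory (consent or Visit 2), and an SAE or death in a screen failure never dosed appears in no planned AE, SAE or death listing

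*SAP*

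**What the plan says.** **Start of AE recording.** Protocol 11.2 has the investigator record events with "start dates occurring any time after informed consent is obtained until 7 days after the last day of study participation". SAP 9.1 repeats that rule. SAP 3.1, describing when assessments are made, refers to "AE recordings, which are completed starting at Visit 2 (Baseline"). In Protocol Table 2-1 and SAP Table 1, the row "Adverse Events Recording" is marked at Visits 2, 3 and 4 and blank at Screening. The Visit 1 procedures in Protocol 10.2.1.1 contain no AE step; the first one is in the Visit 2 list (Protocol 10.2.2). Protocol 11.2 also says: "At each study visit, the investigator will inquire about the occurrence of AE/SAEs since the last visit".

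**Screen failures.** Protocol 14.3 sets the least that must be held on them: "Minimal information includes demography, screen failure details, eligibility criteria, and any SAE". SAP 13.5 says: "Screen failures will only be presented in Listings 16.2.1.1, 16.2.2.1, and 16.2.2.3; otherwise, only enrolled subjects will be listed". Those three are disposition, inclusion and exclusion criteria, and reasons for screen failure. Table 14.3.3.1, the "Subject Listing of Serious Adverse Events", and Table 14.3.3.3, on events leading to death, are assigned to the Safety Population, which SAP 5 limits to subjects who received investigational product.

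**Text pointing the other way in the SAP.** Table 7 labels Listing 16.2.7.1 (Adverse Events) All Subjects, a population that SAP 5 defines from consent and a Screening visit. SAP 6.1.8 says that all collected data will be listed.

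**The concern.** Screening can last up to 35 days, and for some subjects it includes withdrawal of psychotropic or anxiolytic drugs. Protocol 10 counts stopping prohibited therapy among the study-related procedures that need prior consent, and Protocol 9.7.2 says of tapering: "The subject must be consented before any tapering is started". An event during that step happens under the study, so the reader of the study report should be able to find it.

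Two things get in the way. First, sites have two start dates for AE recording. A site working from the schedule may open the AE page only at Visit 2; a site working from Section 11.2 opens it at consent. The treatment-emergent definition has a limb for events that begin before treatment and then worsen, so it needs uniform pre-dose records. Second, the listing rules leave out the subjects whose screening went badly. Exclusion criterion 3 removes subjects judged to be at significant suicidal risk, and eligibility is reviewed at Visit 2 before dosing. A subject who deteriorates during a taper can be screened out for that reason and so fall outside every AE listing. The omission need not be random with respect to harm.

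**Working it through.** No power or alpha figure is involved. The check is a comparison of texts and one subtraction.

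**Step 1. When does recording start?**
- At informed consent: Protocol 11.2; SAP 9.1.
- At Visit 2: SAP 3.1; Protocol Table 2-1 and SAP Table 1 (marks at three visits, none at Screening); Protocol 10.2.1.1 (no AE step).

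The SAP was written against protocol Version 3.0 and the protocol supplied is Version 4.0, but version lag does not explain the conflict. The SAP disagrees with itself (3.1 against 9.1), the protocol disagrees with itself (11.2 against Table 2-1), and the stated reason for Amendment 3 is the interim analysis.

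**Step 2. Where can an SAE or death appear, for a subject who consents and fails before Visit 2 dosing?**
- Listings 16.2.1.1, 16.2.2.1 and 16.2.2.3: the subject is included, but by title these are not AE listings.
- Listing 16.2.7.1 (Adverse Events): labelled All Subjects, but not among the three exceptions in SAP 13.5. The label alone cannot admit screen failures, because 16.2.1.1 and 16.2.2.1 carry the same label and 13.5 still names them as exceptions.
- Tables 14.3.3.1 and 14.3.3.3: Safety Population. No dose, so not included.

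Result: no planned AE, SAE or death listing shows the event.

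**Step 3. The same question for a subject later dosed and enrolled.**
- The Visit 2 inquiry looks back to the previous visit, so a screening-period event can be picked up.
- SAP 9.1 flags treatment-emergent events in the AE listings; it does not select on them.
- The title of Table 14.3.3.1 is not limited to treatment-emergent events, and the subject is in the Safety Population.

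Result: the event can be listed. It is lost only if the site follows the Visit 2 start and does not record it.

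**Step 4. How many subjects?** The protocol synopsis and SAP 3.2 plan 400 screened and 208 randomized.
- Not randomized: 400 − 208 = 192.
- Share of those screened: 192 / 400 = 48%.

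This is an upper bound. Protocol 10.2.2 lets some subjects receive the Visit 2 dose and then be discharged without randomization; they are in the Safety Population and so in Tables 14.3.3.1 and 14.3.3.3. Others may fail at Visit 1 with almost no time under observation. The documents give neither the split, nor the number who taper, nor an event rate.

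**The case against.** The strongest reply is that SAEs are captured and reported whatever the listings show. Protocol 11.2.6.1 requires all SAEs to reach the safety vendor within 24 hours. Protocol 14.3 requires any SAE to be held for a screen failure, and 14.4.3 requires case report forms for everyone who signs consent. Protocol 8.3 requires contact with subjects who miss visits, to rule out an AE as the cause. Screening is itself a study visit, so the inquiry rule in 11.2 arguably applies there. All of this stands: the gap is in the schedule and the planned outputs, not in expedited reporting.

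It can also be said that the SAP has not settled on exclusion. Table 7 labels Listing 16.2.7.1 All Subjects, SAP 6.1.8 promises that all collected data will be listed, and a death might show as a reason in the disposition listing, whose columns are not given. That stands as far as it goes. It makes the SAP inconsistent, and the 13.5 sentence is the more specific rule. SAP 9.1.2 says that deaths and serious AEs will be listed, but it sits in a section based on the Safety Population, so little weight rests on it. Protocol 14.3 concerns information to be held and does not itself prescribe a listing; even so, the plan provides no AE or SAE listing for an item it requires to be collected.

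A reader might infer more: that every serious event during screening and taper drops out of the report. The documents do not support that, because subjects later dosed and enrolled are not barred (Step 3). Nor is the population one selected for suicidal risk: exclusion 3 removes significant risk, and Protocol 7.2 describes the C-SSRS as precautionary.

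**Conclusion.** The concern holds in two limited parts.

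1. The start of AE recording is contradictory within each document. This affects how pre-dose events are captured in every subject.
2. Under SAP 13.5 and the Safety Population definition, an SAE or death in a subject who fails screening before Visit 2 dosing appears in no planned AE, SAE or death listing. This sits against Protocol 14.3, the All Subjects label on Listing 16.2.7.1, and SAP 6.1.8.

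The second part touches at most 192 of 400 screened subjects (48%), and the true number is probably smaller, since that figure includes anyone dosed at Visit 2 but not randomized. It rests on two readings: that the explicit 13.5 sentence governs over the population label in Table 7, and that the three permitted listings, judged by their titles, carry no AE data. SAP 13.5 also refers to enrolled subjects without defining the term, so the place of subjects dosed at Visit 2 but not randomized in the 16.2 listings is unclear.

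No efficacy endpoint, treatment comparison or expedited report is affected. The defect lies in consistent capture and in the completeness of the study report, and it should be corrected before the SAP is applied.

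**What to change.** - Mark AE recording at Screening in Protocol Table 2-1 and SAP Table 1, and add an AE step to Protocol 10.2.1.1 that runs from consent and applies at screen failure.
- Change SAP 3.1 so that AE recording starts at informed consent, matching SAP 9.1 and Protocol 11.2.
- In SAP 13.5, add Listing 16.2.7.1 to the listings that include screen failures, as its population label already implies, and define enrolled.
- Run Tables 14.3.3.1 and 14.3.3.3 on All Subjects, with pre-dose events flagged as not treatment-emergent. State this as an exception to the Safety Population rule that opens SAP 9.

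The cost is some extra AE entry for screen failures, a population change in the listings, and wording changes in both documents. No visit, procedure or efficacy analysis changes.
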